#### 8.2 Alternatives to Participation

There are no alternatives to participation in this pragmatic before/after implementation research study.

#### 8.3 Minimization of Risks

Federal regulations at 45 CFR 46.111(a)(1) require that risks to subjects are minimized by using procedures which are consistent with sound research design. We will review the electronic medical record of all Code Sepsis activations for potential adverse effects related to study procedures. This will include review of standardized Code Sepsis documentation incorporated into clinical care as part of the care redesign. While there are no foreseeable effects of data collection on the care of patients who receive standard care at the control hospitals (all study phases) or during the pre-intervention phase at Intermountain Medical Center, monitoring of aggregate data quality will include all hospitals and study phases. As necessary, after consultation with the Independent Safety Monitor, study procedures (including the Code Sepsis protocol) will be adjusted or even halted if important adverse effects are

identified. There are several specific elements of study design inherent in the present protocol that meet this human subject protection requirement.

#### 8.3.1 Protections against invasion of privacy or breach of confidentiality

Protection of subject identity and prevention of unintentional release of protected information is of paramount importance to the research team.

- Data storage and transfer: Data will be maintained in password-protected, encrypted research servers, REDCap (a secure, HIPAA-compliant system), or password-protected, encrypted computers. Patient identifiers for prehospital data linkage in Aim I will be provided in secure, encrypted electronic format to Department of Health staff for identification of ambulance patient care reports. Matched records will be returned in secure, encrypted electronic format. All devices will have been approved by Intermountain Healthcare or (during matching of ED data to prehospital data) the Utah Department of Health for use with clinical and research data. Both Intermountain and the State of Utah deploy comprehensive information technology support systems to maintain and regularly update computer systems and maintain physical and electronic safeguards for data management. Any paper case report forms will only include study identification numbers, and will be stored in a locked file cabinet. Datasets used for statistical analyses will be deidentified.
- Data access: Only the PI and the study team will have access to identifying information. All individuals with access to identifiable data will have all necessary human subjects training, including Good Clinical Practice training as required by NIH policy for applicable study team members involved in the clinical trial proposed.
- Training: All study personnel will maintain appropriate training in human subjects research and data protection. The PI, primary mentor, and study staff responsible for study coordination, data collection, and data management of the associated clinical trial will maintain Good Clinical Practice training as per NIH policy (NOT-OD-16-148).

#### 8.3.2 Incidental findings

Data review and analysis will use only data collected as part of routine clinical care and operations. We therefore do not expect identification of incidental findings relevant to patient care.

#### 8.3.3 Protection against medicolegal risk

Data on subjects studied in the proposed aims will be kept confidential in accordance with applicable laws and statues.

#### 8.3.4 Optimization of Code Sepsis targeting

Optimization of team activation mechanism during phase #2 of Aim III (intervention run-in and optimization) will help maximize false positive and minimize false negative team activations.

#### 8.3.4 Protections against overtreatment and anchoring bias

Physicians and other providers will be educated intensively about the protocol, with particular emphasis on the corresponding concepts that (1) a sepsis team activation does not establish a sepsis diagnosis and (2) that the sepsis prediction tool was specifically not designed to capture all patients with sepsis and that, as a consequence, many patients with sepsis will not trigger a Code Sepsis.

#### 8.3.5 Protections against overtreatment and adverse drug reactions

Part of this redesign of standard care is incorporation of both direct pharmacist involvement in the Code Sepsis team and antibiotic stewardship monitoring of antibiotic-treated Code Sepsis patients to reduce antibiotic overtreatment. Pharmacist involvement will also help minimize the risk of preventable adverse drug or allergic reactions.

#### 8.4 Potential Benefits of the Proposed Research to Human Subjects and Others

This study has the potential to generate important findings for patients with sepsis and their treating clinicians, including methods to identify sepsis patients at ED triage or in the prehospital setting. Sepsis patients treated in the intervention ED after implementation of the full Code Sepsis protocol could receive faster evaluation, diagnosis, and treatment initiation, leading to improved patient outcomes. The risks to patient confidentiality and the risks for adverse drug reactions appear substantially less than the potential benefit to sepsis patient subjects and the important knowledge gained about delivery of ED sepsis care.

#### 8.5 Importance of the Knowledge to be Gained

Patients with sepsis —a syndrome defined by infection associated with acute organ dysfunction — have high mortality. This syndrome is also common, affecting nearly 3% of ED patients in our data. Early antibiotic initiation improves sepsis outcomes, but many ED patients do not receive timely antibiotics. The overall hypothesis of this phase 2a study is that reorganizing standard ED sepsis care around multidisciplinary "Code Sepsis" teams activated prior to or immediately upon patients' ED arrival will reduce door-to-antibiotic times. Aim III of this proposal will determine whether the Code Sepsis protocol is feasible, safe, and effective at decreasing door-to-antibiotic time. Data from human subjects are also necessary to validate triage- or prehospital-based sepsis prediction models that can be customized by users planning sepsis screening, intensive resource mobilization (as is planned here) for sepsis care, or to aid risk/benefit decisions for sepsis treatments with more than minimal risks (Aim I) and to understand how practice patterns or systems of care may be optimized to accelerate time-dependent treatment while minimizing unintended consequences (Aim II). The no-more-than-minimal risks to subjects from observational research (Aims I and IIA), interviews (Aim IIB), or systematically reorganizing sepsis care to accelerate evaluations and treatments patients would receive anyway under current standard care (Aim III) are acceptable in the context of the important knowledge to be gained to improve care for the common and deadly sepsis syndrome.

## 9. HUMAN SUBJECTS

We will prospectively assess the effect of a system-level intervention on the organization of ED sepsis care using an augmented pre-/post-intervention design. In the post-intervention period, the studied intervention — early activation of ED teams for patients likely to have sepsis — will be adopted as standard care at Intermountain Medical Center. As such, no patients arriving to any ED during the pre-intervention or to a non-intervention control ED will be exposed to the intervention. Conversely, all patients arriving to the Intermountain Medical Center ED in the post-intervention phase will be exposed to the intervention.

#### 9.1 Selection of Subjects

Federal regulations at 45 CFR 46(a)(3) require the equitable selection of subjects. All eligible patients will be enrolled. Study exclusion criteria neither unjustly exclude classes of individuals from participation in the research nor unjustly include classes of individuals from participation in the research. Hence, the recruitment of subjects conforms to the principle of distributive justice.

#### 9.2 Waiver of Informed Consent and HIPAA Authorization

To allow analysis of patient outcomes in all patients during both the pre- and post-intervention phases and to facilitate future research through creation of a research registry, we will request a waiver of informed consent and HIPAA authorization based on the following criteria as per 45 CFR 46.116(d) and the HIPAA Privacy Rule.

#### 9.2.1 Research and registry involve no more than minimal risk

Acceptance is widespread for protocols using pre-arrival notification to activate ED teams for the treatment of other critical illnesses where time-to-treatment determines outcomes. Since the tested exposure will be incorporated into ED care processes as standard care, and will merely accelerate evaluation, testing, and treatment sepsis patients would receive during current (pre-intervention) standard care, patients will overall experience only the risks associated with standard ED clinical care. Research and registry creation involve no direct contact between the study team and patients, only review of records routinely collected for administration and medical care. For a small number of subjects, there will be anonymized monitoring of ED operations in the form of non-interactive observation of Code Sepsis protocol completion involving collection of anonymous data, which would be standard during implementation of any approach to improving standard ED care.

#### 9.2.2 No adverse effects on the rights and welfare of participants

Exposure to standard care in the form of the Code Sepsis protocol and research team abstraction of data routinely collected in the course of clinical care should have no influence on the welfare of study subjects. Analysis and registry storage of data recorded as part of routine clinical care and operations should have no influence on the welfare of study subjects. Because risk is minimal given this design, the waiver of consent and authorization will not adversely affect the rights or welfare of subjects.

# *9.2.3 The research and registry could not practicably be carried out without waiver of informed consent*

Given the large number of eligible patient subjects (up to 530,000, including approximately 9,450 patients with sepsis in the primary analysis cohort), the research and registry could not practicably be carried out without the waiver of consent. The sample size for this chart review is large enough that including only those data for which consent could be obtained would prohibit conclusions to be drawn

and would compromise the scientific validity of the study, as a large proportion of the data would be eliminated if obtaining consent were a requirement. Obtaining consent would also preclude rapid initiation of the Code Sepsis protocol and rapid antibiotic initiation. The subjects whose records will be reviewed will not be followed beyond their hospitalization (except for routine use of data on long-term mortality obtained via existing linkages) and would be mostly lost to follow up. The proportion of subjects who have relocated or have passed away will likely be a significant percentage of the subject population, and so the research results would not be meaningful and would lose statistical power if obtaining consent were a requirement.

#### 9.2.4 Information on the Code Sepsis protocol and study will be available to all ED patients

We will make available patient information sheets describing the Code Sepsis protocol in the intervention emergency department (e.g. lobby, patient information stations, and on request). It is otherwise not possible to provide patient subjects with information about the study as there is no feasible mechanism by which to notify subjects, attempting to do so would substantially increase the risk of a confidentiality breach, and because the information that is found will have no impact on subjects' clinical care.

#### 9.2.5 The minimal necessary amount of protected information will be obtained

Only data necessary for the completion of the study will be collected. The patient ID, encounter ID, social security number, address, and date of birth are necessary to allow data linkage, identification of the specific patient encounter for supplemental data abstraction. Event date/times are necessary for care process and outcome measurement, including calculation of the elapsed time related to various patient management actions include the primary outcome. Identifiers will maintained in the registry to facilitate future research.

#### 9.2.6 All data, including PHI, will be securely guarded from improper disclosure

High-level safeguards will be in place to protect subject identity and confidential data, including in data maintained in the research registry. The study and registry data will be kept on encrypted, passwordprotected computers. These computers are routinely used for storage of patient data and research data including subject identifiers. The data will only be accessible to members of the research team, and all members of the research team have completed Human Subjects Protections and understand the importance of protecting subject privacy and confidentiality. No PHI will be recorded on the CRFs for the study dataset. Protected health information will not be reused or disclosed to any other person or entity, except as required by law, for authorized oversight of the research project, for other research as approved by an IRB, or for other research for which the use or disclosure of protected health information would be permitted by under applicable regulations. Minimal identifiers will be maintained linked to the data. Maintaining minimal identifiers linked to the data is necessary to allow (1) manual abstraction of additional data from the electronic medical record and (2) potential future linkage – with IRB approval -- of the data to additional datasets. No individual subject data will be presented in any presentation, publication or report related to this research. Data will be presented only in anonymized or aggregate or as results of statistical analyses and will not include any individual-level data that could be traced to a particular subject.

## **10. MONITORING AND SAFETY REPORTING**

On the basis of established precedents in implementation research, using toolkits supplied by NIH institutes and the University of Washington's CTSA-supported Institute for Translational Health Sciences and in consultation with the Intermountain Institutional Review Board (IRB) and National Institutes of Health (NIH) staff, we believe the proposed clinical trial represents no more than minimal risk to exposed patients. The study will thus be overseen by an Independent Safety Monitor (ISM), a practicing ICU physician with extensive experience performing clinical trials but not affiliated with the current trial.

#### 10.1 Potential Risks and Benefits for Participants

- Potential risks: The risk level associated with this study is estimated to be no more than minimal, since the studied intervention prehospital activation of ED-based Code Sepsis teams will be adopted as standard care and is designed to accelerate evaluation, testing, and treatments that the patient would have eventually received under current standard care. While the efficient coordination of therapies is novel and likely to improve care overall, we will monitor for the possibility of effects potentially relevant to faster antibiotic therapy, specifically receipt of antibiotics to which the patient is known to be allergic. This possibility is protected against through inclusion of a pharmacist in the Code Sepsis team. Other risks are also minimal and related to loss of confidentiality of data.
- Potential benefits: The potential benefits to study subjects with sepsis treated in the intervention ED after implementation of the full Code Sepsis protocol include faster evaluation, diagnosis, and treatment initiation leading to improved patient outcomes.

#### 10.2 Adverse Event and Serious Adverse Event Collection

#### 10.2.1 Adverse event

A clinical trial adverse event is any untoward medical event associated with the use of the study procedure, whether or not it is considered related to a drug or study procedure. After Code Sepsis intervention, adverse events related or possibly related to study procedures must be evaluated by the PI. The PI, with assistance from study co-investigators as needed, will assess whether there is a reasonable possibility that the study procedure caused the event, based on the criteria below. Investigators will also consider whether the event is unanticipated or unexplained given the patient's clinical course, previous medical conditions, and concomitant medications. If the severe adverse event is judged to be reportable, as outlined below, then the investigator will report to the ISM and IRB his assessment of the potential relatedness of each adverse event to protocol procedure.

The study uses the following AE attribution scale:

- Definitely Related: The event follows: a) A reasonable, temporal sequence from a study procedure; and b) Cannot be explained by the known characteristics of the patient's clinical state or other therapies; and c) Evaluation of the patient's clinical state indicates to the investigator that the experience is definitely related to study procedures.
- Probably or Possibly Related: The event should be assessed following the same criteria for "Definitely Associated". If in the investigator's opinion at least one or more of the criteria are not present, then "probably" or "possibly" associated should be selected.
- Probably Not Related: The event occurred while the patient was on the study but can reasonably be explained by the known characteristics of the patient's clinical state or other therapies.

- Definitely Not Related: The event is definitely produced by the patient's clinical state or by other modes of therapy administered to the patient.
- Uncertain Relationship: The event does not meet any of the criteria previously outlined.

#### 10.2.2 Serious Adverse Event (SAE)

An SAE is any AE that results in any of the following outcomes:

- Death
- A life-threatening experience (that is, immediate risk of dying)
- Event requiring prolongation of existing hospitalization. As per http://www.fda.gov/Safety/MedWatch/HowToReport/ucm053087.htm: Report if admission to the hospital or prolongation of hospitalization was a result of the adverse event. Emergency room visits that do not result in admission to the hospital should be evaluated for one of the other serious outcomes (e.g., life-threatening; required intervention to prevent permanent impairment or damage; other serious medically important event).
- Persistent or significant disability/incapacity. As per http://www.fda.gov/Safety/MedWatch/HowToReport/ucm053087.htm: Report if the adverse event resulted in a substantial disruption of a person's ability to conduct normal life functions, i.e., the adverse event resulted in a significant, persistent or permanent change, impairment, damage or disruption in the patient's body function/structure, physical activities and/or quality of life.
- Important medical events that may not result in death, be life-threatening, or require hospitalization may be considered serious adverse events when, based upon appropriate medical judgment, they may jeopardize the patient and may require medical or surgical intervention to prevent one of the outcomes listed in this definition.

#### 10.2.3 Adverse event monitoring

The PI will review potential adverse events monthly for patients for whom the Code Sepsis protocol was activated during the patient's ED visit. The PI will also review within 72 hours of identification any potential anaphylaxis cases occurring within 24 hours of ED antibiotic initiation in Code Sepsis patients. Adverse events will be monitored via review of the medical record for the first 3 days after Code Sepsis activation or until hospital discharge, whichever occurs first, regardless of the investigator's opinion of causation. Thereafter, serious adverse events are not required to be collected unless routine clinical care monitoring or the PI believes that the event was possibly, probably, or definitely to the Code Sepsis protocol.

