#### 3.7.2 Secondary outcomes

- Clinical/patient-centered secondary outcomes (measured among all ED sepsis patients):
  - 1) All-cause mortality to day 30
  - 2) All-cause mortality to 1 year
  - 3) In-hospital all-cause mortality
  - 4) Hospital charges: Amount charged to patient for their medical care during index ED visit and associated hospitalization.
  - 5) Hospital length of stay
- Process/feasibility secondary outcomes
  - 1) Code Sepsis activation rate: Measured as the percentage of all ED patients for whom the Code Sepsis protocol was activated.
  - 2) Code Sepsis activation accuracy metrics. Accurate Code Sepsis activation is defined as activation for patients who have sepsis while in the ED and no activation for patients who do not have sepsis in the ED.
- Adverse effects and unintended outcomes of protocol implementation

- 1) Antibiotic utilization percentage: measured as the fraction of (1) all ED patients; (2) Code Sepsis activation patients; or (3) "likely" sepsis patients who received IV or IV-equivalent antibiotics.
- 2) Antibiotic spectrum: Total Stenehjem antibiotic spectrum score for all antibiotics administered in first 24 hours, measured for (1) all ED patients or (2) sepsis patients
- 3) Antibiotic overtreatment rate: Percentage of "sepsis mimic" patients who received IV or IVequivalent antibiotics in the ED.
- 4) New onset C. difficile colitis incidence: Percentage of (1) all ED patients and (2) ED sepsis patients with a positive stool test for *Clostridium difficile* colitis between 72 hours and 90 days after ED arrival.
- 5) Adverse drug & allergic reaction incidence: Measured as the fraction of 1) all ED patients and (2) ED sepsis patients with a discharge diagnosis code consistent with anaphylaxis or with an adverse reaction to antibiotics (see Appendix C).
- Potential exploratory outcomes
  - 1) Measures of organ failure trajectory, to include change in the SOFA score between hospital day 1 and hospital day 3, and overall and organ-specific measures of organ failure-free days through day 28.

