#### 6.3 Active Follow-Up for Patients Undergoing Code Sepsis

Via the electronic medical record, a member of the study team will actively monitor Code Sepsis activation patients every 1-3 days until hospital day #7. There will be no direct patient contact.

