#### 8.1.3. Risks to patients exposed to the Code Sepsis protocol

Patients presenting to the intervention hospital during phases #2 and 3 (run-in implementation and full implementation) will be exposed to and may receive care using the "Code Sepsis" version of standard care. The Code Sepsis protocol is designed to accelerate evaluation, testing, and treatments that the patient would have eventually received under now current standard care. The Code Sepsis intervention is therefore expected to pose no more than minimal risks to ED patients exposed to the protocol, including specifically sepsis patients for whom the Code Sepsis protocol is activated. The potential risks to subjects due to this protocol include:

- 1) Adverse drug reactions or antibiotic-associated infections related to unnecessary or overtreatment antibiotic treatment with prespecified regimens.
- 2) Delay in diagnosis of non-infectious problems due to focus on sepsis or infection related to Code Sepsis activation.
- 3) Delay in care related to resource allocation away from non-Code Sepsis patients without sepsis (bystanders without sepsis).
- 4) For sepsis patients for whom the Code Sepsis protocol is not activated (i.e. bystanders with sepsis), delay in care related to lower index of suspicion for sepsis leading to delayed diagnosis or resource allocation away from these patients.

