#### 10.3 Adverse Event and Serious Adverse Event Reporting

We emphasize in AE reporting for this study that the intervention under study is an expedited bundling of established elements of clinical care. Study-specific clinical outcomes of sepsis and ED clinical care are exempt from adverse event reporting *unless* the investigator deems the event to be related to the administration of study drug or the conduct of study procedures (or of uncertain relationship). The following are examples of events that will be considered routinely recorded clinical outcomes:

- Death not related to study procedures.
- Adverse drug reaction (excluding anaphylaxis associated with antibiotic administration) not related to study procedures
- Secondary and healthcare associated infections
- Persistent or progressive organ failure

• Prolonged hospitalization

The PI will report to the ISM within 72 hours of identification all AEs that are serious and possibly, probably, or definitely related to study procedure (or of uncertain relationship) or are unexpected. If the ISM concurs with the PI's assessment, the AE will be reported to the IRB within 7 business days. Other AEs will be reviewed by the PI on a monthly basis and reported in aggregate to the ISM on a quarterly basis. A summary report on all adverse events will be submitted to the IRB during annual recertification as per IRB guidelines. Good Clinical Practice will be followed for conduct of the study.

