#### **10.4 Interim Analysis**

There will be no interim analyses.

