#### 10.5.2 Enrollment, procedure, regulatory, and data quality monitoring

Our data monitoring plan will include

- 1. Review of accrued data at monthly study team meetings
- 2. Review of data safety and interim data analysis performed by the independent safety monitor
- 3. Semi-annual audits of study materials by the Intermountain PCCM regulatory affairs group
- 4. An annual review performed by the Intermountain Healthcare IRB

Careful monitoring of the data collection, regulatory adherence, data quality, and study procedures will help to protect the safety of study subjects, the quality of data, and the integrity of the study. The PI or study staff will review all data collection on an ongoing basis for data completeness and accuracy as well as protocol compliance. Data verification for key demographic, exposure, and outcome parameters will be performed on an ongoing basis for a random 5% of all Code Sepsis patients. This will occur on the basis of data reabstraction by someone other than the individual who originally collecting the data or by blinded duplicate data entry. The results of the ongoing data review will be incorporated into each review with the ISM. A statement reflecting the results of the ongoing data review will be incorporated into the annual report for the IRB.

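### Routine adverse-event review ends about when the C. difficile outcome window opens, so a rise in this named risk has no scheduled route to the safety monitor during the trial

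*Protocol*

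**What the plan says.** **The risk.** The first item in the protocol's list of risks to exposed patients (section 8.1.3) is "Adverse drug reactions or antibiotic-associated infections related to unnecessary or overtreatment antibiotic treatment with prespecified regimens".

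**The outcome.** Section 3.7.2 counts a positive stool test for C. difficile "colitis between 72 hours and 90 days after ED arrival". The SAP carries this as a safety outcome in the sepsis and all-patient cohorts. It leaves out patients who tested positive in the 14 days before arrival or within 72 hours after it.

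**Adverse-event review.** Section 10.2.3 monitors records "for the first 3 days after Code Sepsis activation or until hospital discharge, whichever occurs first", whatever the investigator thinks of causation. After that, attribution decides: "Thereafter, serious adverse events are not required to be collected unless routine clinical care monitoring or the PI believes that the event was possibly, probably". The sentence closes with the strongest grade of attribution.

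**Reporting.** Section 10.3 lists "Secondary and healthcare associated infections" among clinical outcomes that are not reported as adverse events, unless the investigator judges the event related or of uncertain relationship.

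**A second follow-up window.** Section 6.3 says a member of the study team "will actively monitor Code Sepsis activation patients every 1-3 days until hospital day #7".

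**Interim review.** Section 10.4 states "There will be no interim analyses". Section 10.5.2 lists "Review of data safety and interim data analysis performed by the independent safety monitor" as part of the monitoring plan.

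**The concern.** The safety plan and the outcome definition look at different periods. The one stretch in which adverse events are recorded regardless of cause is almost wholly outside the period in which new C. difficile can count. From day 3 or discharge, a case enters the safety system only if someone notices it and believes it related.

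That is a weak filter for this kind of harm. Patients given antibiotics have some background rate of C. difficile, so an excess caused by overtreatment would show as a difference in rates between sites and phases, not as a feature of any one case. The protocol also holds that Code Sepsis only speeds up care patients would have had anyway (sections 8.1.3 and 9.2.1), which makes a single case easy to judge unrelated. Two other statements point the same way:

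- Section 10.1 narrows the specific monitoring target to antibiotics the patient is known to be allergic to.
- Section 10.5.1 bases safety monitoring on ED quality assurance and incident reports, which are poorly placed to pick up a stool test weeks later.

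At stake is whether the monitor, who is relied on to spot a safety signal, routinely sees data on a risk the protocol itself puts first.

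**Working it through.** The plan gives no figure to reproduce. The check is how far the two windows overlap, followed by an illustration of scale.

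**1. Overlap of the windows**

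- Adverse-event window (section 10.2.3): 0 to 72 hours from activation, cut short at discharge.
- C. difficile window (section 3.7.2 and SAP): 72 hours to 90 × 24 = 2,160 hours from ED arrival. Length: 2,160 − 72 = 2,088 hours, or 87 days.
- With activation L hours after arrival, the adverse-event window closes at 72 + L hours from arrival, so the overlap is (72 + L) − 72 = L hours at most.

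The documents do not give the time from door to activation, so L is an assumed range:

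| L | Maximum overlap | Share of 2,088 h |
|---|---|---|
| 0 min | 0 h | 0% |
| 30 min | 0.5 h | 0.02% |
| 60 min | 1 h | 0.05% |
| 120 min | 2 h | 0.10% |
| 240 min | 4 h | 0.19% |

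A patient discharged before 72 hours has no overlap.

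**2. If section 6.3 counts as adverse-event surveillance**

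Taking hospital day 7 to end at 144 or 168 hours, the overlap is 144 − 72 = 72 hours (3 days, 3.4% of 87 days) or 168 − 72 = 96 hours (4 days, 4.6%). If monitoring stops at discharge, this holds only for patients still in hospital. Section 6.3 does not say that its monitoring is for adverse events.

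**3. Illustrative scale**

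- Roll-in phase, November 13, 2019 to February 12, 2020: 92 days. With 4.5 sepsis patients a day and 30% activation (section 7.3): 92 × 4.5 × 0.30 ≈ 124. Section 7.3 gives the 30% for the full-implementation phase; using it here is an assumption.
- Full-implementation phase: 1,650 × 0.30 = 495.
- Activated sepsis patients in all: 124 + 495 = 619.
- No C. difficile rate is given. At an assumed 1% to 3% over 90 days: 619 × 0.01 ≈ 6 to 619 × 0.03 ≈ 19 cases.

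These are total cases, not an excess due to Code Sepsis. The 619 leaves out activated patients without sepsis, who are the group most relevant to overtreatment. Over 15 months, or five quarters, 6 to 19 cases is about 1 to 4 per quarter.

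**4. Routes to the monitor**

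| Route | Covers C. difficile after day 3? |
|---|---|
| Routine record review (10.2.3) | No |
| Late serious event (10.2.3) | Only if believed related |
| 72-hour report of serious events (10.3, 10.5.1) | Only once identified, and judged related, uncertain or unexpected |
| Quarterly aggregate of other adverse events (10.3) | Only if the case was recorded as an adverse event |
| Reports on request (10.5) | Yes, if the monitor asks |
| Interim data analysis (10.5.2) | Content not stated; conflicts with 10.4 |

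No row is a scheduled C. difficile count.

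**The case against.** A reader might infer that C. difficile is exempt from reporting, that it cannot prompt a halt, or that the signal is compiled only in the final analysis. The documents do not support any of these.

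- The exemption in section 10.3 lapses when an event is judged related or of uncertain relationship, and the attribution scale in section 10.2.1 makes a possible or probable rating easy to reach.
- Serious events that are related, uncertain or unexpected go to the monitor within 72 hours of identification (sections 10.3 and 10.5.1).
- Section 10.5 lets the monitor end the study on any important safety signal and entitles the monitor to requested reports. Section 8.3 allows procedures to be adjusted or halted.
- Section 10.5.2 provides for monthly review of accrued data and some interim review by the monitor.
- Section 10.5 refers to a safety monitoring charter that is not among the documents. It may say what the monitor receives.

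It can also be said that the controlled comparison at 90 days is better evidence than individual attribution, that the study is described as minimal risk, that quarterly counts will be small, and that sections 6.3 and 10.2.3 may serve different purposes.

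All of this limits the point without removing it. The late routes depend on someone recognizing and attributing a case, or on the monitor asking. That a controlled comparison is more informative is a reason to show the monitor such a comparison, not a reason to leave it until the end. If the two follow-up windows have different purposes, the protocol should say so.

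**Conclusion.** The point holds as a gap in scheduled information. Routine adverse-event review shares 0% to 0.19% of the C. difficile window for activation up to 240 minutes after arrival (an assumed range). Even on the generous reading of section 6.3 the share is 3.4% to 4.6%. Because healthcare-associated infections are routine outcomes by default, a rise in this named risk would reach the monitor during the trial only through ad hoc recognition and attribution, or on request. The monitor's power to act is intact.

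Sections 6.3 and 10.2.3 give different follow-up windows for the same patients, and sections 10.4 and 10.5.2 contradict each other. Both pairs must be reconciled.

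The overlap result rests on the stated windows alone, apart from the activation lag. The 6 to 19 cases are only an illustrative total under an assumed 1% to 3% rate, and the conclusion does not depend on them. The unseen charter could narrow the gap. This is a cheap improvement to oversight and does not affect the primary analysis.

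**What to change.** 1. Reconcile protocol sections 6.3 and 10.2.3, stating which follow-up of activated patients is for adverse events and which is for other data.
2. Reword section 10.4 to exclude interim efficacy analysis only, so that it agrees with section 10.5.2.
3. Add to the existing quarterly report to the monitor an electronic count, by site and phase, of the C. difficile outcome already defined in the SAP. Antibiotic use in the sepsis mimic cohort, also already defined, could be added.
4. State in section 10.3 that C. difficile in activated patients is included in that report, whatever the judgment on individual relatedness.

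The cost is protocol wording and one recurring data-warehouse query. It needs no patient contact and spends no alpha on the primary outcome. There are two limits. Counts will be small (about 1 to 4 a quarter among activated sepsis patients in the illustration), so the report shows accumulating numbers and will seldom separate a rise from chance in a single quarter. And the latest 90 days will be incomplete at each review, so the report should show how many patients have completed follow-up.
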